Melatonin will be provided by the study. However, oral DMT will be provided by the subject's specialty pharmacy and paid by the subject or the subject's insurance.

E. Outcome Measures

- 1. Primary Outcome
 - i. Change in urinary 6-SMT in 24 hours urine
- 2. Secondary Outcomes:
 - i. Change in Serum morning Melatonin level
 - ii. Change in MFIS

iii. Change in MSIS-29

iv. Change in PSQI

v. Number of Relapses during enrollment

vi. Change in PDDS-PS

F. Methods

- 1. Subject Selection
- a. Inclusion Criteria
 - i. Male and female subjects with relapsing forms of MS who have been on a stable dose of dimethyl fumarate, fingolimod, teriflunomide, diroximel fumarate, siponimod, or ozanimod for 6 months or longer
 - ii. Confirmed diagnosis of Relapsing MS

iii. Ages 18 to 65 who are able to provide informed consent

- iv. Women of childbearing potential must employ proven methods to prevent pregnancy during the course of the trial; the acceptable method will be left to the judgment of the investigator
- v. Not pregnant or lactating
- vi. No evidence of significant cognitive or psychiatric disorder
- vii. Able to understand the purpose and risks of the study

viii. Must be willing to sign an informed consent and follow the protocol requirements

b. Exclusion Criteria

i. Use of melatonin within 30 days of enrollment

- ii. The addition of any sleep aide or change in dose within 30 days of enrollment or during the trial
- iii. The addition or change in dose of Vitamin D within 30 days of enrollment or during the trial
- iv. Change in DMT during the trial
- v. Steroid therapy within 30 days of enrollment
- vi. Use of anticoagulation at the time of enrollment and during the trial
- vii. The addition of an antidepressant is not allowed during the study period; if on an antidepressant at screening, the dose must be stable 30 days prior to enrollment and dose changes are prohibited during the study

- viii. The addition or change in dose of any stimulants, including but not limited to, amantadine, armodafinil, methylphenidate, or modafinil within 30 days of enrollment or during the trial
- 2. Discontinuation of Subjects from the Study
 - i. Subjects may voluntarily withdraw consent and discontinue their participation in the study at any time
 - ii. If a subject has a relapse during the study, the study doctor may discontinue melatonin and/or oral DMT

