 - a. A relapse is defined as a new symptom, or worsening of pre-existing neurologic symptoms, of at least 24 hours duration, in subjects who had been clinically stable for the prior 30 days, in the absence of fever, sleep deprivation or severe emotional stress.
 - iii. Subject has an adverse event that presents unacceptable risk, per investigator discretion
 - iv. Subject has inadequate adherence to the protocol, per investigator discretion
 - v. Subject is lost to follow-up
 - vi. Subject becomes pregnant
- 3. Method of Treatment Assignment

The randomization sequence will be generated using R statistical software and will be stratified by age group and gender with a 1:1 allocation using a fixed block size of four. The following four strata will be used: 1) younger females, 2) older females, 3) younger males, and 4) older males. As subjects enter the study, they will be designated to a stratum and will be assigned either a 3 mg or 5 mg melatonin dose based on the pre-generated randomization scheme within that stratum. A master list containing drug kit numbers and drug assignment will be kept in a password-protected computer file in the research pharmacy. The investigator, study coordinator and subjects will remain blinded until study completion. The blind will only be violated if, in the judgment of the treating investigator, unblinding is necessary for subject safety.

4. Study Treatment

- i. All subjects will continue their oral DMT and start the study drug on Day 1 (Baseline Visit).
- ii. Oral DMT will be taken per standard of care dosing and paid for by the subject/subject insurance.
- iii. Subjects randomized to melatonin will take either 3mg once a day or 5mg once a day. Melatonin will be supplied by Thorne Pharmaceuticals. The study drug will be taken at 21:00 each day ±2 hours.

5. Concomitant and Excluded Therapy

The addition of a sleep aide is not allowed during the study period. If subjects were on a sleep aide prior to the trial, no change in this medication is allowed and the dose must be stable 30 days prior to enrollment.

No change in Vitamin D supplementation will be allowed during the study and the dose must be stable 30 days prior to enrollment.

The addition of an antidepressant is not allowed during the study period. If on an antidepressant at screening, the dose must be stable 30 days prior to enrollment and dose changes are prohibited during the study.

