Stimulants, amantadine, armodafinil, methylphenidate or modafinil cannot be added during the study period. If subjects were on any of these listed medications prior to the trial, no change in this medication is allowed and the dose must be stable 30 days prior to enrollment.

The enrolling investigator is to review prior and concomitant medications at screening to ensure concomitant and excluded therapy requirements are met.

6. Study Assessments

The investigator or designated research staff will obtain informed consent from each subject after explaining the purpose of the study and the potential risks and benefits known or can be reasonable expected. The IRB approved informed consent will be signed by the subject before any screening assessments or procedures are performed.

The serum melatonin level will be drawn in the morning (09:00±2 hours).

- i. Assessments During Treatment
 - a. Visit 1 or Screening Visit (1-30 days prior to baseline)
 - i. Informed consent
 - ii. Inclusion/exclusion criteria review
 - iii. Demographic Information
 - iv. Vital signs (including height and weight at screening)
 - v. Review of concomitant medications
 - vi. Review of all prior medications taken within last 30 days
 - vii. Medical history
 - viii. MS history
 - ix. Childbearing potential review
 - x. Physical exam [If a subject had a physical exam during the screening window (1-30 days prior to baseline) with a trial investigator but it was completed

prior to consent as part of standard of care, the data from this exam may be used for the screening visit physical exam requirement. This is allowed only if all elements of the required exam were completed.]

- xi. Neurological exam [If a subject had a neurological exam during the screening window (1-30 days prior to baseline) with a trial investigator but it was completed prior to consent as part of standard of care, the data from this exam may be used for the screening visit neurological exam requirement. This is allowed only if all elements of the required exam were completed.]
- xii. Oral DMT compliance assessment
- xiii. Vitamin D laboratory level (the most recent vitamin D laboratory level that was collected as part of standard of care, not to be ordered specifically for trial)
- xiv. Dispense lab collection materials/instructions for Urinary 6sulfatoxymelatonin collection (24-hr urine collection), specimen to be collected within -3 days of visit 2 and returned to clinic at visit 2

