- xv. Adverse event assessment (starting after informed consent obtained)
- xvi. Telephone contact-remind subject to complete 24 hour collection within -3 days of visit 2 (to be completed within -5 days of visit 2, not applicable/required if screening and baseline are 1 day apart)
- b. Visit 2 or Baseline Visit (Day 1)
 - i. Urine collection (within -3 days of visit 2)
 - 1. Urinary 6-SMT collection will begin and continue for 24 hours
 - ii. Vital signs
 - iii. Serum melatonin level collection (09:00±2 hours)
 - iv. Review of concomitant medications
 - v. Dispense Subject Dosing Diary
 - vi. Adverse event assessment
 - vii. Relapse assessment
 - viii. MFIS
 - ix. MSIS-29
 - x. PSQI
 - xi. PDDS-PS

- xii. Oral DMT compliance assessment
- xiii. Vitamin D laboratory level (if collected since the last trial visit as part of standard of care, not to be ordered specifically for trial)Inclusion/exclusion criteria review
- xiv. Randomization
- xv. Dispense study drug-first dose at 21:00 ±2 hours on Day 1
- xvi. Dispense lab collection materials/instructions for Urinary 6sulfatoxymelatonin collection (24-hr urine collection), specimen to be collected within -3 days of visit 3 and returned to clinic at visit 3
- xvii. Telephone contact-study medication compliance, verify study drug first dose date/time (within +3 days of visit 2)
- xviii. Telephone contact-remind subject to complete 24 hour collection within -3 days of visit 3 (to be completed within -5 days of visit 3)
- c. Visit 3 (3 months +/- 14 days from baseline)
 - i. Urine collection (within -3 days of visit 3)
 - 1. Urinary 6-SMT collection will begin and continue for 24 hours
 - ii. Vital signs
 - iii. Serum melatonin level collection (09:00±2 hours)
 - iv. Review of concomitant medications
 - v. Adverse event assessment
 - vi. Relapse assessment
 - vii. MFIS
 - viii. MSIS-29
 - ix. PSQI
 - x. PDDS-PS
 - xi. Physical exam
 - xii. Neurological exam
 - xiii. Study medication compliance and accountability assessment
 - xiv. Collect study medication and dispense new study medication
 - xv. Oral DMT compliance assessment

- xvi. Vitamin D laboratory level (if collected since the last trial visit as part of standard of care, not to be ordered specifically for trial)Collect and dispense new Subject Dosing Diary

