If discontinuation of oral DMT and/or melatonin occurs and the subject is unwilling to continue in the trial for observation, an ET visit must be performed within 7 days after the last dose of oral DMT and/or melatonin (date of whichever is stopped first, if both discontinued).

- i. Urine collection (±3 days of visit ET)
 - 1. Urinary 6-SMT collection will begin and continue for 24 hours

- ii. Vital signs
- iii. Serum melatonin level collection (09:00±2 hours)
- iv. Review of concomitant medications
- v. Adverse event assessment
- vi. Relapse assessment
- vii. MFIS
- viii. MSIS-20
- ix. PSQI
- x. PDDS-PS
- xi. Physical exam (only required if subject was last examined more than 6 months ago or per treating physician's discretion)
- xii. Neurological exam (only required if patient was last examined more than 6 months ago or per treating physician's discretion)
- xiii. Study medication compliance and accountability assessment
- xiv. Collect study medication
- xv. Oral DMT compliance assessment
- xvi. Vitamin D laboratory level (if collected since the last trial visit as part of standard of care, not to be ordered specifically for trial)Collect Subject Dosing Diary
- g. Unscheduled Visits(UNS)

Subjects will be instructed to contact their treating investigator in the event of a relapse and may be asked to return for an UNS visit. Additionally, an UNS visit will be completed within 7 days after the last dose of oral DMT and/or melatonin (date of whichever is stopped first, if both discontinued) if stopped between visits and the subject is willing to continue in the trial for observation.

- i. Urine collection (±3 days of visit UNS)
 - 1. Urinary 6-SMT collection will begin and continue for 24 hours
- ii. Vital signs
- iii. Serum melatonin level collection (09:00±2 hours)
- iv. Review of concomitant medications
- v. Adverse event assessment

- vi. Relapse assessment
- vii. MFIS
- viii. MSIS-29
- ix. PSQI
- x. PDDS-PS
- xi. Physical exam (only required if a relapse is suspected or per treating physician's discretion)
- xii. Neurological exam (only required if a relapse is suspected or per treating physician's discretion)
- xiii. Study medication compliance and accountability assessment
- xiv. Oral DMT compliance assessment
- xv. Vitamin D laboratory level (if collected since the last trial visit as part of standard of care)
- xvi. Collect and dispense new Subject Dosing Diary
- h. Discontinuation of study drug
 - i. If the subject becomes pregnant

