- Possibly Any reaction that follows a reasonable temporal sequence from administration of investigational drug *OR* that follows a known response pattern to the suspected drug *AND* that could not be reasonably explained by the known characteristics of the subject's clinical state or other modes of therapy administered to the subject.
- Related Any reaction that follows a reasonable temporal sequence from administration of investigational drug *AND* that follows a known response pattern to the suspected drug *AND* that recurs with re-challenge, *AND/OR* is improved by stopping the drug or reducing the dose.

Investigator Reporting Responsibilities for Safety and Monitoring

- Monitor and record all adverse events
- Determine the seriousness, causality, and severity of each adverse event
- Form a Data Safety Monitoring Board (DSMB) and conduct regular meetings to review safety findings
- Report all serious adverse events to the FDA according to the code of federal regulations
- Actively and persistently pursue follow-up of serious adverse events
- Submit annual reports to study sponsor
- J. Estimated Duration of the Study and Critical Timeline Elements
 - a. IRB Approval April 26th, 2018
 - b. Study Start Date– May 9th, 2018
 - c. Enrollment Completion Date, Estimated November 9th, 2020
 - d. Study Completion Date, Estimated November 9th, 2021

Table 1: Schedule of Events

Visit Number	Visit 1	тс	Visit 2 ^A	тс	тс	Visit 3	тс	Visit 4	тс	Visit 5	Visit ET	Visit UNS
Visit Schedule	Screening 1-30 Days prior to Baseline	Within -5 days of Visit 2	Baseline Day 1	Within +3 days of Visit 2	Within -5 days of Visit 3	Month 3 к ±14 days	Within -5 days of Visit 4	Month 6 к ±14 days	Within -5 days of Visit 5	Month 12 ^к ±14 days		
Informed Consent	х											1
Inclusion/Exclusion Review	Х		Х									
Demographic Information	Х											
Vitals ^B	Х		Х			Х		х		Х	Х	Х
Height and Weight	Х											
Prior Medication Review	Х											
Concomitant Medication Review	Х		Х			Х		Х		Х	Х	Х
Adverse Event Assessment	Хм		Х			х		Х		Х	Х	Х
Medical History	Х											
MS History	Х											
Childbearing Potential Review ^c	Х											
Physical Exam	Xa					х		х		Х	XN	Xo
Neurological Exam	X ^R					х		Х		Х	XN	Xo
Urinary 6-SMT reminder		X٢			Х		Х		Х			
Urinary 6-SMT Collection D			Х			Х		Х		Х	Х	Х
Dispense 24hr Urine Collection Materials	Х		Х			х		х				
Serum Melatonin Collection ^E			Х			Х		Х		Х	Х	Х
Standard of Care Vitamin D Level ^P	Х		Х			х		х		Х	Х	Х

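### Contraception is required throughout and pregnancy stops study drug, but no pregnancy or contraception check is scheduled in the up to 374 days after baseline

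*Combined protocol and SAP*

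**What the plan says.** The rules:

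- F.1.a.iv sets a requirement for the whole trial: "Women of childbearing potential must employ proven methods to prevent pregnancy during the course of the trial". The choice of method is left to the investigator.
- F.1.a.v requires that a subject be "Not pregnant or lactating".
- F.2.vi gives as a reason for discontinuing a subject: "Subject becomes pregnant".
- F.6.i.h.i gives as a reason for discontinuing study drug: "If the subject becomes pregnant".

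The scheduled checks:

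- Screening (F.6.i.a, item ix) lists "Childbearing potential review". In Table 1 the row "Childbearing Potential Review" is marked at Visit 1 only. Its footnote C deals with the choice of method and specifies no repeat.
- Baseline (F.6.i.b) lists "Inclusion/exclusion criteria review". The entry runs on from the vitamin D line at item xiii and comes just before randomization. Table 1 marks this row at Visits 1 and 2.
- The lists for Visits 3, 4 and 5, early termination (ET) and unscheduled (UNS) visits name neither pregnancy nor contraception. They do include adverse event and concomitant medication reviews. Physical exams are scheduled at months 3, 6 and 12 and are conditional at ET and UNS.
- No pregnancy test is listed at any visit.

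**The concern.** The protocol makes contraception a standing condition and pregnancy a trigger for stopping, but schedules nothing after baseline that is directed at either. A subject can conceive while on study drug and complete every listed assessment without being asked. If the pregnancy is recognised late, the stop that the protocol itself calls for also comes late, and so does any safety follow-up.

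This looks like an oversight because the other whole-trial rules have a recurring check. The restrictions on sleep aids, vitamin D, antidepressants, stimulants and anticoagulation can be verified at the medication review of every visit. The oral disease modifying therapy has its own compliance item at every visit. Section I.c also counts a congenital anomaly or birth defect as a serious adverse event, so the plan recognises the outcome but schedules no look for the exposure.

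What is at stake is subject safety and the working of a stop rule. Type I error, power and sample size are not affected; the protocol gives no sample size calculation.

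**Working it through.** The protocol states no figure for this interval, so there is none to reproduce. The intervals follow from its own visit windows.

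**Inputs**

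- One month is 30 days (Table 1, footnote K).
- Visits 3, 4 and 5 are at months 3, 6 and 12, each with a window of 14 days either side, counted from baseline (F.6.i.c to e; Table 1).
- The last scheduled check of criteria iv and v is the eligibility review at Visit 2 (F.6.i.b; Table 1).

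**Step 1: last scheduled check to last visit**

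- Earliest Visit 5: 12 × 30 − 14 = 346 days after baseline.
- Latest Visit 5: 12 × 30 + 14 = 374 days after baseline.

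The period without a scheduled check is therefore 346 to 374 days for a subject who completes the trial.

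**Step 2: longest intervals between consecutive visits**

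| Interval | Formula | Longest (days) |
|---|---|---|
| Baseline to Visit 3 | 90 + 14 | 104 |
| Visit 3 to Visit 4 | (180 + 14) − (90 − 14) = 194 − 76 | 118 |
| Visit 4 to Visit 5 | (360 + 14) − (180 − 14) = 374 − 166 | 208 |

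**Step 3: rules set against scheduled checks**

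| Rule | Screening | Baseline | Visits 3, 4, 5, ET, UNS |
|---|---|---|---|
| Contraception (F.1.a.iv) | childbearing review and eligibility review | eligibility review | none named |
| Not pregnant (F.1.a.v) | eligibility review | eligibility review | none named |
| Stop on pregnancy (F.2.vi, F.6.i.h.i) | – | – | none named |

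The text lists and Table 1 agree, so the gap is not an artefact of one of them being incomplete.

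**Step 4: effect of asking at every existing visit**

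If status were recorded at Visits 3, 4 and 5, the longest time without a scheduled check would fall from 374 days to 208 days, the Visit 4 to Visit 5 interval. The only telephone contact scheduled in that interval is the urine-collection reminder within 5 days before Visit 5. A question added there would come at the earliest 208 − 5 = 203 days after Visit 4 in the longest case, so it would change little.

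**The case against.** A reader who looks only at the childbearing row of Table 1 might infer that status is checked once, at screening, and count 30 + 360 + 14 = 404 days to the last visit. The sum is right for the row of that name, but the inference is not supported. The eligibility review at Visit 2 covers criteria iv and v again before randomization, so a pregnancy known by then fails criterion v. Only one not yet recognised could pass, and asking about status would not catch that either.

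A reader might also infer that detection depends wholly on the subject volunteering the information. That is too strong. Every later visit has an adverse event review and a medication review, where a change in hormonal contraception could surface. Exams take place at months 3, 6 and 12, and subjects are given site telephone numbers (section H.b). None of these contacts is specified for this purpose, so whatever they reveal is incidental. The consent form was not available for this review and may tell subjects to report a pregnancy.

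It can fairly be said that a trial-long requirement, a stop rule and a schedule without a repeat check do not strictly contradict one another. That stands: this is an omission, not an inconsistency. It can also be said that asking at existing visits leaves the longest interval, between Visits 4 and 5, as long as before. That stands too.

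**Conclusion.** The point holds. Pregnancy and contraception status are reviewed at screening and at baseline, and then not again by any scheduled item for up to 374 days. Within that period up to 208 days can pass between Visits 4 and 5. A safety stop rule is left without a scheduled check of its trigger.

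The day counts rest on the protocol's 30-day month and visit windows, and on reading the Visit 2 eligibility review as covering all the criteria, including iv and v. The documents give neither the share of subjects who are women of childbearing potential nor a pregnancy rate, so no expected number of pregnancies is offered and the conclusion does not depend on one.

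The change is worth making because it is cheap and concerns subject safety. It has no bearing on the planned statistical analyses.

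**What to change.** Reconcile F.1.a.iv and v, F.2.vi and F.6.i.h.i with the visit lists and Table 1. Carry the existing childbearing row to Visits 3, 4, 5, ET and UNS, and add the matching item to each of those visit lists, with current contraception and pregnancy status recorded. Visit 2 needs no new item, because its eligibility review already covers these criteria. Contraceptive method and any testing stay with the investigator.

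The cost is five more marks in one row of Table 1, one case report form question and about a minute per visit for the women concerned. No new visit, sample or staff is needed. The amendment should not be presented as closing the gap: it gives the stop rule a scheduled check at each existing visit, but the interval of up to 208 days between Visits 4 and 5 remains.

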Fatigue is one of the most disabling symptoms in patients with multiple sclerosis, affecting approximately 90% of patients with MS^{11} . There are multiple reasons for this fatigue, but poor sleep is a contributing factor. Treatment naïve MS patients have demonstrated a reduction in 24 hour urinary 6-sulfatoxymelatonin (6-SMT)¹². In the same study, the levels increased when interferon- β treatment was added with a trend in improving fatigue.

B. Research Strategy:

To date, there are no published data on the role of melatonin supplementation or the appropriate dose for patients with multiple sclerosis. Because of the potential benefits of melatonin, this pilot study will be an exploratory investigation to evaluate the effect of supplementing melatonin in subjects with multiple sclerosis who are taking an oral disease modifying therapy (DMT) for 6 months or longer. It is our intent that the results of this study will support the rationale and be a prelude to a larger trial which can focus on clinical efficacy of melatonin therapy outcomes.

C. Research Objectives

1. The primary objective of this study is to evaluate the change in 24 hour urinary 6-SMT collected for 24 hours in two twelve hour sessions.

2. The secondary objectives are to evaluate the change in serum morning melatonin level. In addition, quality of life (QOL) measures will be assessed including the Modified Fatigue Impact

Scale (MFIS)¹³, Multiple Sclerosis Impact Scale (MSIS-29)¹⁴, and the Pittsburgh Sleep Quality Index (PSQI)¹⁵. Clinical objectives include the number of relapses during the trial and a change in the Patient Determined Disease Steps & Performance Scales (PDDS-PS).¹⁶⁻¹⁹

D. Study Design

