The proposed pilot study is a one-year randomized, rater- and dose-blinded trial evaluating the potential role of melatonin in subjects with relapsing multiple sclerosis who have been taking a stable dose of an oral DMT for at least 6 months. The oral DMTs include dimethyl fumarate, fingolimod, teriflunomide, diroximel fumarate, siponimod, and ozanimod. Thirty subjects with relapsing forms of multiple sclerosis who meet all of the eligibility criteria will be enrolled at Providence Neurological Specialties in Portland, Oregon. The subjects will be consented by the investigator or delegated research personnel before undergoing any study procedures. Subjects will be randomized to melatonin 3 mg, or melatonin 5 mg. There will be 15 subjects in each group. As this is a pilot study, we do not include a sample size calculation.

Urinary and serum melatonin testing will be conducted at baseline, month 3, month 6, month 12, and any early termination or unscheduled visits. Subject reported measures for the assessment of fatigue, QoL, sleep, and MS severity (MFIS, MSIS-29, PSQI, and PDDS-PS) will be administered at baseline, month 3, month 6, month 12, and any early termination or unscheduled visits. Relapses during the study will be documented and recorded. If the subject does have a relapse, they will be treated per our clinical protocol which consists of Solu-Medrol 1 gram IV once a day for 3 to 5 days depending on the severity of symptoms.

If discontinuation of oral DMT and/or melatonin occurs, the subject may continue in the trial for observational purposes. An unscheduled (UNS) visit will be completed within 7 days after the last dose of oral DMT and/or melatonin (date of whichever is stopped first, if both discontinued). They will complete all applicable visits items moving forward (urinary 6-SMT reminder, urinary 6-SMT collection, dispense 24- hour urine collection materials, serum melatonin collection, dispense subject dosing diary, dispense study drug, study medication compliance/accountability, and potentially oral DMT compliance assessment will no longer be relevant/required). If oral DMT and/or melatonin is discontinued and the subject is unwilling to stay on the study for observational purposes, an early termination visit must be performed within 7 days after the last dose date of whichever is stopped first.

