 - ii. At the discretion of the investigator for medical or ethical reasons
 - iii. If the subject withdrawals consent
 - iv. If the subject is unwilling or unable to comply with the protocol, per investigator discretion
- G. Statistical Methods

Subject characteristics for each arm will be reported for continuous variables (mean, standard deviation, median, and range) and categorical variables (counts and percentages). All analyses will use two-sided tests at the 0.05 significance level. This study is based on an intention to treat model, in which all subjects receiving at least one dose of melatonin will be included.

a. Primary Analysis

Longitudinal analyses using a linear mixed models for repeated measures will be used to compare changes in 24-hour urinary 6-sulfatoxymelatonin and serum morning Melatonin over time between arms. Each outcome will be treated as continuous and identify link functions will be used. Overall trajectories as well as the mean change from baseline to 3, 6, and 12 months for each arm will be reported and compared.

b. Secondary Analysis

Changes in the MFIS, MSIS-29, PSQI, & PDDS-PS from baseline to 3, 6, and 12 months will be reported and tested using a paired t or Wilcoxon signed-rank test for related samples. Twosample t or Mann-Whitney tests will be used to compare change between arms at each time point. The mean number of relapses during enrollment for each arm will be reported and compared using a Poisson analysis. Kaplan-Meier survival analysis methodology will be used to estimate the proportion of subjects relapse-free at months 3, 6, and 12 and log rank tests will be used to compare arms.

To examine agreement between 24-hour urinary 6-sulfatoxymelatonin and serum morning melatonin level, the measurements will be plotted and compared using prediction intervals from regression analysis as outlined in 2003 paper by J. M. Bland and D. G. Altman²⁰.

H. Regulatory

a. Regulatory Requirements

The study will be performed in accordance with ICH GCP Guidelines and the Code of Federal Regulations for clinical research. Any amendments to the study protocol must be approved by Providence Health and Services Institutional Review Board before implementation. AEs and protocol violations or deviations must be reported according to the guidelines of Providence Health and Services Institutional Review Board.

b. Safety Assessments

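### Randomisation is stratified by age group and gender, but the between-dose comparisons in Section G name neither factor; if the factors predict change, the tests are conservative and lose modest precision.

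*Combined protocol and SAP*

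**What the plan says.** Section F.3 (Method of Treatment Assignment) says the randomisation sequence "will be stratified by age group and gender with a 1:1 allocation using a fixed block size of four". It adds: "The following four strata will be used: 1) younger females, 2) older females, 3) younger males, and 4) older males". The age that separates younger from older is not given.

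Section G.a (Primary Analysis) covers urinary 6-SMT and serum melatonin: "Longitudinal analyses using a linear mixed models for repeated measures will be used to compare changes in 24-hour urinary 6-sulfatoxymelatonin", and "Overall trajectories as well as the mean change from baseline to 3, 6, and 12 months for each arm will be reported and compared". It names no covariates and no covariance structure. It also does not say whether the baseline value is one of the repeated responses.

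Section G.b (Secondary Analysis) covers MFIS, MSIS-29, PSQI and PDDS-PS: "Twosample t or Mann-Whitney tests will be used to compare change between arms at each time point". Section G sets the level for everything: "All analyses will use two-sided tests at the 0.05 significance level".

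On purpose and size, Section B states that "this pilot study will be an exploratory investigation to evaluate the effect of supplementing melatonin in subjects with multiple sclerosis". Section D states: "There will be 15 subjects in each group. As this is a pilot study, we do not include a sample size calculation".

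**The concern.** Stratified blocks force the arms to be nearly equal on age group and gender. If those factors predict change, the variation they cause largely drops out of the difference between arms. An unadjusted test does not know this and still counts that variation as residual noise. Its standard error is then too large for the design used, and it rejects less often than the stated 5%.

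For the four scales the gap is definite, because neither named test can take a covariate. For the two mixed models the plan is silent: it neither includes the factors nor rules them out.

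What is at stake is precision, not validity. The estimate of the dose difference stays unbiased and the type I error is not inflated. If the factors affect only the level of an outcome and not its change, single-visit tests on change lose nothing. The point does not extend to the Poisson analysis of relapses, the log rank test or the within-arm paired tests.

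**Working it through.** The plan states no power, effect size or SD, so there is no figure of its own to reproduce.

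**Inputs from the documents:** 15 per arm (Section D); four strata, 1:1, blocks of four (Section F.3); two-sided 0.05 (Section G).

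**Assumed, because the documents are silent:** SD of change 1; true dose difference 1 SD; R² (the share of variance in change explained by the two factors) from 0 to 0.3; additive effects split equally between the factors; half younger; 75% female unless stated.

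**Step 1: hand calculation for the t test**, taking arms exactly balanced within strata and normal change.

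- Unadjusted SE = √(2/15) = 0.365.
- SE that fits the design = 0.365 × √(1 − R²).
- Unadjusted type I error ≈ P(|t₂₈| > 2.048/√(1 − R²)). At R² 0.2: 2.048/0.894 = 2.29, and P(|t₂₈| > 2.29) = 3.0%.
- Power: noncentrality = 1/(0.365 × √(1 − R²)). The adjusted test uses 26 df and critical value 2.056. The unadjusted test uses 28 df and the raised critical value above.

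| R² | Design SE | Unadjusted SE too large by | Unadjusted type I error | Power, unadjusted to adjusted |
|---|---|---|---|---|
| 0 | 0.365 | 0% | 5.0% | 75.3% to 75.1% |
| 0.1 | 0.346 | 5% | 4.0% | 76.4% to 79.4% |
| 0.2 | 0.327 | 12% | 3.0% | 77.6% to 83.8% |
| 0.3 | 0.306 | 20% | 2.1% | 79.0% to 88.3% |

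**Step 2: simulation of the actual allocation**, with incomplete blocks (5,000 runs per setting; 10,000 for the mixed model). The t test is compared with a linear model containing arm, age group and gender. Mann-Whitney is compared with the same linear model on ranked change. The mixed model has a random intercept, visits at 0, 3, 6 and 12 months, complete data, effects constant from month 3, residual intraclass correlation 0.5, and baseline as a response. Its target is the month-12 change contrast, adjusted through factor-by-visit terms.

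Power (%), unadjusted to adjusted, normal change:

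| R² | t test | Mann-Whitney | Mixed model |
|---|---|---|---|
| 0 | 75.4 to 74.3 | 72.3 to 72.6 | 77.0 to 76.2 |
| 0.05 | 75.6 to 76.6 | 72.7 to 74.9 | 78.8 to 78.9 |
| 0.1 | 77.2 to 79.8 | 73.5 to 76.8 | 79.1 to 80.4 |
| 0.2 | 76.9 to 83.5 | 73.1 to 81.4 | 83.4 to 86.1 |
| 0.3 | 76.9 to 87.6 | 73.3 to 85.0 | 84.8 to 89.4 |

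Unadjusted type I error at R² 0.1, 0.2 and 0.3 is 3.8%, 3.0% and 2.1% for the t test, and 4.8%, 4.2% and 3.4% for the mixed model. Mann-Whitney runs at 1.4% to 3.8% over the error shapes tried. Over all settings the adjusted linear model holds 3.9% to 5.2% and the adjusted rank model 4.4% to 5.6%.

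**Step 3: other assumptions.**

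- Mann-Whitney to adjusted rank model at R² 0.2: 88.8% to 94.0% with t₃ errors, 89.0% to 93.9% with lognormal errors, 70.6% to 78.5% with heavily tied scores.
- 50% female at R² 0.2: t test 77.4% to 83.9%, mixed model 82.1% to 84.9%.
- A separate simulation (20,000 replicates, 70% female, 1.06 SD difference) gave unadjusted t-test type I error of 4.0%, 3.1% and 2.3% at R² 0.1, 0.2 and 0.3. Power rose from 81.0% to 83.4%, 81.9% to 87.6% and 82.8% to 90.9%. At R² 0 it went from 79.5% to 78.9%.

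**The case against.** The strongest case is that no harm is documented. Nothing in the protocol says that age or gender predicts change in any of these outcomes, and at R² 0 there is nothing to recover. Even at R² 0.05 the gains are only 1.0 point (t test), 2.2 (Mann-Whitney) and 0.1 (mixed model). The trial is an exploratory pilot with no power target to miss. This stands. It keeps the importance modest and the claim conditional.

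The gain is also smallest for the primary outcome, which uses the mixed model, and Section G does not rule adjustment out there. This stands too, although the small gain depends on the random-intercept covariance assumed here. With complete data and an unstructured covariance, the contrast at each visit behaves like the single-visit t test, so the gain would be larger. Section G does not say which structure applies.

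Finally, the simulated effects are additive, which suits a two-factor adjustment. If all the stratum effect were an age-by-gender interaction, the two-factor model would gain essentially nothing: at R² 0.3 the t test goes from 77.6% to 77.1% and the rank version from 73.3% to 74.7%. That is an extreme case, and adjustment does almost no harm in it.

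None of this removes the asymmetry. The sponsor chose these two factors for balance, using them costs about a point of power at worst, and Section G still plans 5% tests between doses at every visit.

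**Conclusion.** The concern holds as a modest but worthwhile improvement. As written, the t and Mann-Whitney tests are conservative and less precise than the design allows whenever age group or gender predicts change. The mixed models share the problem if fitted without these factors.

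For R² from 0.1 to 0.3 and a 1 SD difference, adjustment gains about 3 to 12 points of power in single-visit tests and 1 to 5 in the random-intercept mixed model. Over the whole R² range from 0 to 0.3, the effect runs from a loss of about 1 point to a gain of about 12. These sizes rest on the assumed R², stratum mix, error shapes and additive effects. The direction follows from the design. With 15 per arm and results meant to inform a larger trial, the precision is worth having.

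**What to change.** State in Section G, before unblinding, that between-dose comparisons of change adjust for age group and gender, coded by the cut used for randomisation. Give that cut, because Section F.3 does not.

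- **Urinary 6-SMT and serum melatonin:** name the form of the mixed model. If post-baseline change is the response, add the two factors as main effects. If baseline is a repeated response, add age group-by-visit and gender-by-visit terms. Main effects alone then leave the change contrast as it was (SE ratio 1.000 with complete data, 0.997 to 1.000 with 15% of follow-up missing, at R² 0.2).
- **Scales, where the t test would be used:** a linear model for change with arm, age group and gender.
- **Scales, where Mann-Whitney would be used:** keep a rank-based analysis, for example the same linear model on ranked change. A raw-scale linear model in its place would lose power with skewed or heavy-tailed change: at R² 0, from 90.8% to 81.0% (t₃) and from 91.9% to 78.2% (lognormal).
- **Two factors rather than four strata:** a four-stratum van Elteren test costs 2 to 5 points against Mann-Whitney at R² 0 (72.3% to 67.6% with normal errors, 90.8% to 88.4% with t₃, 91.9% to 89.5% with lognormal).

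The cost is a few sentences in Section G; both variables are already recorded. Each comparison spends two parameters, or eight (two factors × four visits) if baseline is a response. If the factors predict nothing, the loss is 0.2 to 1.1 points for the t test, 0.5 to 0.8 for the random-intercept mixed model, and none beyond simulation error for the rank analysis. The rank model gives a p value and no difference in scale units, so the planned descriptive changes should stay.
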